10.1.6. Data Quality Assurance

- All participant data relating to the study will be recorded on printed or electronic CRF unless transmitted to the sponsor or designee electronically (e.g., laboratory data). The investigator is responsible for verifying that data entries are accurate and correct by physically or electronically signing the CRF.

- The investigator must maintain accurate documentation (source data) that supports the information entered in the CRF.
- The investigator must permit study-related monitoring, audits, IRB/IEC review, and regulatory agency inspections and provide direct access to source data documents.
- Monitoring details describing strategy (e.g., risk-based initiatives in operations and quality such as Risk Management and Mitigation Strategies and Analytical Risk-Based Monitoring), methods, responsibilities and requirements, including handling of noncompliance issues and monitoring techniques (central, remote, or on-site monitoring) are provided in the monitoring plans.
- The sponsor or designee is responsible for the data management of this study including quality checking of the data.
- The sponsor assumes accountability for actions delegated to other individuals (e.g., Contract Research Organizations).
- Study monitors will perform ongoing source data verification to confirm that data entered into the CRF by authorized site personnel are accurate, complete, and verifiable from source documents; that the safety and rights of participants are being protected; and that the study is being conducted in accordance with the currently approved protocol and any other study agreements, ICH GCP, and all applicable regulatory requirements.
- Records and documents, including signed ICFs, pertaining to the conduct of this study must be retained by the investigator as stated in the clinical trial agreement. No records may be destroyed during the retention period without the written approval of the sponsor. No records may be transferred to another location or party without written notification to the sponsor.

10.1.7. Source Documents

- Source documents provide evidence for the existence of the participant and substantiate the integrity of the data collected. Source documents are filed at the investigator's site.
- Data reported on the CRF or entered in the eCRF that are transcribed from source documents must be consistent with the source documents or the discrepancies must be explained. The investigator may need to request previous medical records or transfer records, depending on the study. Also, current medical records must be available.
- Definition of what constitutes source data can be found in the study procedures manual.

10.1.8. Study and Site Start and Closure

The sponsor or designee reserves the right to close the study site or terminate the study at any time for any reason at the sole discretion of the sponsor. Study sites will be closed upon study completion. A study site is considered closed when all required documents and study supplies have been collected and a study-site closure visit has been performed.

The investigator may initiate study-site closure at any time, provided there is reasonable cause and sufficient notice is given in advance of the intended termination.

CONFIDENTIAL
AGN-241622

Reasons for the early closure of a study site by the sponsor or investigator may include but are not limited to:

- Failure of the investigator to comply with the protocol, the requirements of the IRB/IEC or local health authorities, the sponsor's procedures, or GCP guidelines
- Inadequate recruitment of participants by the investigator
- Discontinuation of further study intervention development

If the study is prematurely terminated or suspended, the sponsor shall promptly inform the Investigators, the IECs/IRBs, the regulatory authorities, and any contract research organization(s) used in the study of the reason for termination or suspension, as specified by the applicable regulatory requirements. The investigator shall promptly inform the participant and should assure appropriate participant therapy and/or follow-up. If a premature termination or suspension occurs, the sponsor shall remain responsible for providing resources to fulfill the protocol obligations and existing agreements for follow-up of participants enrolled in the study, and each investigator or authorized designee shall promptly inform enrolled participants, if applicable.

10.1.9. Publication Policy

- Allergan as the sponsor has proprietary interest as the sponsor in this study. Authorship and manuscript composition will reflect joint cooperation between multiple investigators and sites and Allergan personnel. Authorship will be established prior to the writing of the manuscript. As this study involves multiple centers, no individual publications will be allowed prior to completion of the final report of the multicenter study except as agreed with Allergan.
- The sponsor will comply with the requirements for publication of study results. In accordance with standard editorial and ethical practice, the sponsor will generally support publication of multicenter studies only in their entirety and not as individual site data. In this case, a coordinating investigator will be designated by mutual agreement.
- Authorship will be determined by mutual agreement and in line with International Committee of Medical Journal Editors authorship requirements.

10.1.10. Compliance with Protocol

The investigator is responsible for compliance with the protocol at the investigational site. A representative of the sponsor will make frequent contact with the investigator and his/her research staff and will conduct regular monitoring visits at the site to review participant and study intervention accountability records for compliance with the protocol. Protocol deviations will be discussed with the investigator upon identification. Significant protocol deviations will be reported to the IRB/IEC according to the IRB/IEC's reporting requirements.

10.2. Appendix 2: Clinical Laboratory Tests

- The tests detailed in [Table 10-1](#) will be performed by the central laboratory.
- Protocol-specific requirements for inclusion or exclusion of participants are detailed in [Section 5](#) of the protocol. Refer to the Central Laboratory Manual for further details regarding central laboratory collection and shipment procedures.
- Additional tests may be performed at any time during the study as determined necessary by the investigator or required by local regulations. The investigator or qualified site personnel must review all laboratory results for any AEs. Laboratory test results that represent AEs should be reflected on an AE eCRF page. Investigators must document their review of each laboratory safety report.
- Evaluation and management of abnormal laboratory results should be conducted according to local site practice.

Table 10-1 Protocol-Required Safety Laboratory Assessments

Laboratory Assessments	Parameters			
Hematology	Platelet Count	RBC indices: MCV MCH MCHC %Reticulocytes Morphology	WBC count with differential (absolute): Neutrophils Bands Lymphocytes Monocytes Eosinophils Basophils	
	RBC Count			
	Hemoglobin			
	Glycated hemoglobin			
	Hematocrit			
Clinical Chemistry	BUN, uric acid	Potassium	AST	Total, direct, and indirect bilirubin
	Creatinine	Sodium	ALT	Total Protein
	Creatine kinase	Magnesium	Phosphorus	Bicarbonate
	Glucose [fasting]	Calcium	Alkaline phosphatase	Cholesterol, albumin
Routine Urinalysis	
 Specific gravity pH, glucose, protein, blood, ketones, bilirubin, urobilinogen, nitrite, leukocyte esterase by dipstick Clarity, color, and presence of blood Microscopic examination (if blood or protein is abnormal) 			
Other Screening Tests	
 Urine drug screen and alcohol test (to include at minimum: benzoylecgonine [cocaine], methadone, barbiturates, amphetamines, benzodiazepines, cannabinoids, opiates, phencyclidine, and cotinine) at timepoints listed in Sections 1.3.1, 1.3.2, and 1.3.3. Serum human chorionic gonadotropin pregnancy test at screening and urine test at timepoints listed in Sections 1.3.1, 1.3.2, and 1.3.3 (for women of childbearing potential). Serology (HIV type 1 and type 2 antibody, hepatitis B surface antigen, and hepatitis C virus antibody) All study-required laboratory assessments will be performed by a central laboratory, with the exception of the following: 
 Urine dipstick kits may be used to conduct drugs-of-abuse screens and pregnancy tests at the study center post-screening. Alternatively, a breathalyzer may be used for an alcohol screen. 			

10.3. Appendix 3: Adverse Events: Definitions and Procedures for Recording, Evaluating, Follow-up, and Reporting

10.3.1. Definition of AE

AE Definition

- An AE is any untoward medical occurrence in a patient or clinical study participant, temporally associated with the use of study intervention, whether or not considered related to the study intervention.
- NOTE: An AE can therefore be any unfavorable and unintended sign (including an abnormal laboratory finding), symptom, or disease (new or exacerbated) temporally associated with the use of study intervention.

Events Meeting the AE Definition

- Any abnormal laboratory test results (hematology, clinical chemistry, or urinalysis) or other safety assessments (e.g., ECG, radiological scans, vital signs measurements), including those that worsen from baseline, considered clinically significant in the medical and scientific judgment of the investigator (i.e., not related to progression of underlying disease); for example:
 - The test result is associated with accompanying symptoms, and/or
 - The test result requires additional diagnostic testing or medical/surgical intervention, and/or
 - The test result leads to a change in study dosing (outside of any protocol-specified dose adjustments) or discontinuation from the study, significant additional concomitant drug treatment, or other therapy, and/or
 - The test result is considered to be an AE by the investigator or sponsor.
- Exacerbation of a chronic or intermittent pre-existing condition including either an increase in frequency and/or intensity of the condition.
- New conditions detected or diagnosed after study intervention administration even though it may have been present before the start of the study.
- Signs, symptoms, or the clinical sequelae of a suspected drug-drug interaction.
- Signs, symptoms, or the clinical sequelae of a suspected overdose of either study intervention or a concomitant medication. Overdose per se will not be reported as an AE/SAE unless it is an intentional overdose taken with possible suicidal/self-harming intent. Such overdoses should be reported regardless of sequelae.
- The signs, symptoms, and/or clinical sequelae resulting from lack of efficacy will be reported as AE or SAE if they fulfil the definition of an AE or SAE. Also, *lack of efficacy or failure of expected pharmacological action* also constitutes an AE or SAE.

- *Lack of efficacy or failure of expected pharmacological action* per se will not be reported as an AE or SAE. Such instances will be captured in the efficacy assessments. However, the signs, symptoms, and/or clinical sequelae resulting from lack of efficacy will be reported as AE or SAE if they fulfil the definition of an AE or SAE.

Events NOT Meeting the AE Definition

- Any clinically significant abnormal laboratory findings or other abnormal safety assessments which are associated with the underlying disease, unless judged by the investigator to be more severe than expected for the participant's condition. Merely repeating an abnormal test, in the absence of any of the above conditions, does not constitute an AE. Any abnormal test result that is determined to be an error does not require recording as an AE.
- The disease/disorder being studied or expected progression, signs, or symptoms of the disease/disorder being studied, unless more severe than expected for the participant's condition.
- Medical or surgical procedure (e.g., endoscopy, appendectomy): the condition that leads to the procedure is the AE.
- Situations in which an untoward medical occurrence did not occur (social and/or convenience admission to a hospital).
- Anticipated day-to-day fluctuations of pre-existing disease(s) or condition(s) present or detected at the start of the study that do not worsen.

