In Stage 2, participants with presbyopia will be selected to participate in the study. Stage 2 will be further divided into Stages 2a (Cohorts 4 to 6) and 2b (Cohorts 7 and 8). Cohorts 4 to 6 (Stage 2a) will be multiple ascending dose cohorts in which participants will be randomized to receive either AGN-241622 at dose strengths ranging from [REDACTED] or vehicle once daily in both eyes for 14 days. In each cohort in Stage 2a, approximately 12 participants will be randomized in a 3:1 ratio to receive AGN-241622 ophthalmic solution or vehicle in order to evaluate safety, tolerability, pharmacokinetics, and efficacy of AGN-241622 (Figure 1-1). As in Stage 1, the DMC may recommend modifying the proposed dose strength (e.g., de-escalate to a lower dose strength), repeat the current dose strength, modify the cohort size, or stop the study. After Cohort 6 has completed, the DMC will also recommend the dose strength to be tested in Stage 2b.

Cohort 7 is a single-masked, active comparator cohort in which approximately 60 participants with presbyopia will be randomized in a 1:1 ratio to receive either pilocarpine HCl [REDACTED] 1.25% ophthalmic solution or AGN-241622 ophthalmic solution administered at the dose strength recommended by the DMC once daily in both eyes for 14 days. Safety, tolerability, and efficacy of AGN-241622 compared with pilocarpine HCl ([REDACTED] 1.25%) will be assessed after repeat bilateral topical ocular administration. Cohort 8 is an exploratory cohort in which approximately 12 participants with presbyopia who wear contact lenses will be randomized in a 3:1 ratio to receive either AGN-241622 administered at the dose strength recommended by the DMC or vehicle once daily in both eyes for 14 days. Safety, tolerability, tear pharmacokinetics, and efficacy of AGN-241622 administered at the dose strength

CONFIDENTIAL
AGN-241622

recommended by the DMC compared with vehicle will be assessed after repeat bilateral administration.

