8.3. Adverse Events and Serious Adverse Events

The definitions of an AE or SAE can be found in Appendix 3, Section 10.3.

AEs will be reported by the participant.

CONFIDENTIAL
AGN-241622

The investigator and any qualified designees are responsible for detecting, documenting, and recording events that meet the definition of an AE or SAE and any other study-specific terms as relevant and remain responsible for following up AEs that are serious, considered related to the study intervention or study procedures, or that caused the participant to discontinue the study intervention/study (see Section 7).

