8.3.2. Method of Detecting AEs and SAEs

The method of recording, evaluating, and assessing causality of AEs and SAEs and the procedures for completing and transmitting SAE reports are provided in Appendix 3, Section 10.3.

Care will be taken not to introduce bias when detecting AEs and/or SAEs. Open-ended and non-leading verbal questioning of the participant is the preferred method to inquire about AE occurrences.

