10.1. Appendix 1: Regulatory, Ethical, and Study Oversight Considerations

10.1.1. Regulatory and Ethical Considerations

- This study will be conducted in accordance with the protocol and with the following:
 - Consensus ethical principles derived from international guidelines including the CIOMS International Ethical Guidelines
 - Applicable ICH/ISO GCP Guidelines
 - Applicable laws and regulations
- The protocol, protocol amendments, ICF, Investigator Brochure, and other relevant documents (e.g., advertisements) must be submitted to an IRB/IEC by the investigator and reviewed and approved by the IRB/IEC before the study is initiated.
- Any amendments to the protocol will require IRB/IEC approval before implementation of changes made to the study design, except for changes necessary to eliminate an immediate hazard to study participants.
- The investigator will be responsible for the following:
 - Providing written summaries of the status of the study to the IRB/IEC annually or more frequently in accordance with the requirements, policies, and procedures established by the IRB/IEC
 - Notifying the IRB/IEC of SAEs or other significant safety findings as required by IRB/IEC procedures
 - Providing oversight of the conduct of the study at the site and adherence to requirements of 21 CFR, ICH guidelines, the IRB/IEC, European regulation 536/2014 for clinical studies (if applicable), European Medical Device Regulation 2017/745 for clinical device research (if applicable), and all other applicable local regulations

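### Protocol 10.3.1 tells sites both that lack of efficacy is itself an adverse event and that it is not to be reported as one, so TEAE rates could depend on which bullet a site followed

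*Protocol*

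**What the plan says.** Protocol 10.3.1 has two adjacent bullets on lack of efficacy, both placed before the heading for events that do not meet the AE definition. The first closes with: "Also, *lack of efficacy or failure of expected pharmacological action* also constitutes an AE or SAE". The second opens with: "Lack of efficacy or failure of expected pharmacological action* per se will not be reported as an AE or SAE", and says where those cases go instead: "Such instances will be captured in the efficacy assessments". The bullets agree that symptoms or sequelae arising from lack of efficacy are reported when they meet the AE or SAE definition in their own right.

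Other text bears on how the bullets would be read. The list of events that are not AEs includes "The disease/disorder being studied or expected progression, signs, or symptoms of the disease/disorder being studied", unless worse than expected for that participant. Protocol 8.3 says "AEs will be reported by the participant", and 8.3.2 adds: "Open-ended and non-leading verbal questioning of the participant is the preferred method to inquire about AE occurrences".

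On the analysis side, SAP 3.5 keeps two of the four safety endpoints in SAP 3.3: adverse events and clinical laboratory assessments. SAP 8.2.2 reports the number and percentage of subjects with one or more events. SAP 4.0 and 8.1 pool the vehicle groups within each stage.

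**The concern.** The bullets conflict on one case: lack of efficacy with nothing else attached. Under the first it is an AE. Under the second it stays off the AE form. Protocol 8.3.1 requires all AEs to be collected, so a site cannot satisfy both.

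The study is multicenter, and two sites could treat the same remark (a participant saying that the drops did not help is the obvious case) in opposite ways, each in line with the protocol. The resulting difference in TEAE rates would reflect reading of the text and not safety.

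This matters more than usual here for three reasons. AEs are a primary measure in Stages 1 and 2a. The groups are small. And SAP 3.5 and Table 3 in SAP 12.1 leave no efficacy analysis in the synoptic CSR, so a reader would have no efficacy result against which to interpret such a record.

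**Working it through.** **No stated figure to reproduce.** Protocol 9.1 and 9.2 set no hypotheses and no statistical basis for the sample sizes. The check is a reading of the text, followed by simple proportions for scale.

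**Step 1: does any other text settle the conflict?**

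| Place | What it does | Settles it? |
|---|---|---|
| General AE definition, Protocol 10.3.1 | Requires an untoward medical occurrence | Leans to the second bullet; does not cancel the first |
| Exclusion of the disorder under study, Protocol 10.3.1 | Removes expected signs and symptoms of presbyopia | Same |
| Protocol 8.3 and 8.3.2 | Participant reporting, open-ended questions | Makes systematic recording unlikely; does not say what to do with a spontaneous report |
| Protocol 8.3.1 | All AEs are collected | No; it makes the first bullet binding if that bullet is followed |
| TEAE definitions, Protocol 9.4.2.1 and SAP 8.2.1 | Filter on timing or worsening | No |
| Remainder of SAP 8.2 | Overview, SOC/PT tables, discontinuations | No rule for lack-of-efficacy records |

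A lack-of-efficacy record that begins after first dosing would therefore pass into the TEAE tables.

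**Step 2: group sizes.** Protocol 4.1 states for each Stage 2a cohort that "approximately 12 participants will be randomized in a 3:1 ratio". Table 4-1 and SAP Table 1 give 9 active and 3 vehicle in each of Cohorts 4 to 6.

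- Each dose group: 9 planned.
- Pooled Stage 2a vehicle: 3 cohorts × 3 = 9 planned.

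**Step 3: weight of one record.** If k participants in a group of n have a lack-of-efficacy record and no other TEAE, that group's overview TEAE rate rises by 100 × k/n points. Its difference from any other group moves by the same amount.

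- n = 9, k = 1: 100/9 = 11.1 points.
- n = 8, k = 1: 100/8 = 12.5 points (assumed size).
- n = 10, k = 1: 100/10 = 10.0 points (assumed size).
- k = 0: no effect.

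The sizes 8 and 10 are a range I have assumed, because cohort sizes are only approximate. A participant who has another TEAE is already counted, so the record does not move the overview TEAE row.

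**Step 4: what cannot be calculated.** Direction, and any shift beyond one record, depend on non-response rates and on how often sites recorded non-response as an AE. The documents give neither, so I claim neither.

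**Scope.** Section 10.3.1 is not restricted by stage. Failure of pharmacological action could also be recorded in Stage 1, where pupil diameter measures target engagement (Protocol 8.1). Planned Stage 1 sizes are the same, so the same arithmetic applies.

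**The case against.** The strongest reply is that the conflict is lopsided and probably had no consequence. The second bullet is the more specific: it addresses lack of efficacy on its own and names where it is captured. The first gives no threshold, timepoint or measure, so a site has little to act on, and non-response in presbyopia would not ordinarily meet a seriousness criterion. A participant who felt no benefit already has the PGIC, PGIS, PICQ and NVPTQ in which to say so. Stage 2a was double-masked, which makes a failure of expected drug action hard for a site to judge. The 11.1 points is the weight of any single AE in a group of nine, not an estimate of harm from this wording. Such an event would normally appear under its own term in the SOC/PT tables of SAP 8.2.3, and SAP 11.0 plans no testing.

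Most of this stands. It lowers the likelihood of such a record and makes one easier to spot. It does not make the two instructions compatible, and it does not stop a record made under the first bullet from entering the overview percentage. Seeing the term in a SOC/PT table also does not show what the overview rate would have been without it.

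**Conclusion.** The contradiction is explicit and unresolved, and it concerns what counts as an event in a primary safety measure. It should be dealt with before the synoptic CSR is written.

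At planned sizes, each affected participant with no other TEAE moves a group's overview rate by 11.1 points (10.0 to 12.5 for groups of 10 down to 8). This rests on the planned allocation and on pooling vehicle within stage. The realised effect may well be zero, since nothing in the documents shows that a lack-of-efficacy AE was recorded. The output is descriptive, so no inference or error rate is affected. I am confident of the conflict in the text; the effect on the reported rates is conditional on what the AE data contain.

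**What to change.** 1. Search the AE data from Stages 1 and 2a for events recorded solely for lack of efficacy or failure of pharmacological action.
2. Note in the SAP and the synoptic CSR that the protocol text conflicted. If the search finds nothing, one sentence saying so is enough.
3. If it finds any, flag and list them, and show the SAP 8.2.2 overview TEAE percentages with and without them.
4. Before the protocol text is used again, delete the sentence in the first bullet that conflicts with the second. This cannot change past reporting, because SAP 1.0 records that the study ended after Stage 2a was complete.

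The cost is one search and one sentence. A flag, a short listing and one extra overview row are needed only if such events exist. There are no new data and no burden on participants. If the deletion is issued as an amendment, Protocol 10.1.1 applies: "Any amendments to the protocol will require IRB/IEC approval before implementation of changes made to the study design".
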